### **11) Provisions to Monitor the Data to Ensure the Safety of Subjects**

This study does not include more than a minimal level of risk.

### **12) Withdrawal of Subjects**

Patients can be removed from the study without his or her approval if they fail to adhere to the study protocol (i.e., keep scheduled appointments or follow directions) and/or exhibit critical blood pressure readings at study visits (i.e.,  $\geq 180/110$  mmHg) that require close monitoring from his or her primary care doctor.

Patients may withdraw from participation at any time without penalty. Withdrawing from the study will not impact the care that patients receive at the Ambulatory Care Practice. Patients may also withdraw authorization for use or disclose his/her protected health information for the study.

If patients do decide to withdraw consent, they will be asked to contact the principal investigator, [name] to let her know. [name] or another member of the study team will discuss with patients any considerations involved in discontinuing participation in the study. Patients will be informed that already collected data may not be removed from the study database. However, they will be asked whether they intend to withdraw from the entire study (all data collection) or would only like to stop participating in the patient education/counseling calls with the Research Assistant. If the patient agrees to continue with data collection, they will be contacted for the final three month visit to collect the remaining study data. We will also seek permission to collect data from the patient's medical chart. If they agree, this data will be handled the same as research data.

### **13) Risks to Subjects**

This study does not include more than a minimal level of risk. Though we expect the level of risk due to this study to be small, there are some potential risks we would like to make patients aware of:

Elevated blood pressure or blood glucose: One of the reasons patients are eligible for this study is because they have high blood pressure or type 2 diabetes. Although patients are receiving regular care from their primary care doctor while participating in this study, it is possible that their blood pressure or blood glucose might become higher and will require close attention. If this happens, we will refer patients back to their doctor for treatment.

Inconvenience or Discomfort: Patients may feel the study visits are inconvenient. They may also feel uncomfortable answering some of the study questions. Patients can refuse to answer any questions they wish. There is also a minimal risk that being audiotaped may make patients uncomfortable. However, the research team is taking many steps to

ensure that patients do not feel uncomfortable during the audiotaped interview with the Research Assistant. In addition, patients' name will not be transcribed from the audiotapes to ensure that there is no identifiable information included in the report. All audiotapes will be stored in a safe and secure place that only study personnel will be able to access.

Violation of patient's privacy: Because patients' blood pressure and HbA1c recordings, survey responses, and the patient education/tailored adherence sessions will be used as a source of data for this study, there is a potential risk of a violation of privacy. However, the research team is taking many steps to ensure that patients' private information is kept safe. All study visits will be conducted in a dedicated room at the primary care clinic. Additionally, all data will be stored in a safe and secure place that only study personnel will be able to access.

#### **14) Potential Benefits to Subjects**

We cannot promise any immediate benefits to patients from taking part in this research. However, possible benefits include the following: Patients may be more likely to take his or her high blood pressure or anti-diabetic medications as a result of the information they receive during the course of the study. They may also lower their blood pressure and improve their quality of life.

#### **15) Vulnerable Populations**

N/A

#### **16) Sharing of Results with Subjects**

All participating patients can choose to receive their individual adherence profiles and adherence summary reports at the end of the 3-month study.

#### **17) Setting**

All potential subjects will be identified and recruited at the Bellevue Ambulatory Care Practice located on the second floor of Bellevue Hospital Center. All data collection will also be conducted in a dedicated space at the Ambulatory Care Practice. Semi-structured interviews will be conducted in a dedicated private office located on the sixth floor of Bellevue Hospital Center.

**Feasibility of recruitment plan:**

[name] is an Assistant Professor of Medicine at NYU School of Medicine. She has extensive experience working on community- and practice-based trials and training clinic staff in the delivery of patient-centered counseling techniques. She is currently the PI of a NIH/NHLBI-sponsored K23 trial in community-based primary care practices. [name] is a Professor of Medicine at Bellevue/NYU School of Medicine. He is a board-certified internist, hypertension specialist, and an Attending Physician at the Bellevue Hospital Ambulatory Care practice. He also has extensive experience implementing practice-based trials and is the PI of a NIH/NHLBI-sponsored R01 in Bellevue Ambulatory Care clinic. Based on their current work in primary care practices, Drs. [name] and [name] will coordinate involvement of the Medical Director and clinic staff in identification and recruitment of eligible patients as well as coordinate with the study staff to address any logistic issues that may arise in the process of patient screening and enrollment.

Because of our prior record of successful patient recruitment in the Bellevue Ambulatory Care Practice, and the large number of hypertensive patients seen at these practices, we should be able to recruit the 6 patients/month that the study timeline requires. [name] will devote 10% of her time to conducting and completing the research. [name] will devote approximately 2.5% of his time to the project. The research staff ([name] [name] and [name]) will each dedicate 50% of their time to conducting the research.

**Facilities:** This study will take place at the Bellevue Ambulatory Care Practice located within Bellevue Hospital Center. Bellevue employs 25 primary care providers, including internists, family practitioners, nurse practitioners, physician assistants, and bilingual support and administrative staff. [name] currently has an ongoing study at the Ambulatory Care Practice with dedicated space to conduct her research.

**Adherence to the protocol:** To ensure adherence to the study protocol, Drs. [name] and [name] will meet with primary care providers and clinic staff at the study site prior to participant enrollment. The study rationale, its significance and procedures will be explained. Physicians will be given laminated pocket cards that list eligibility criteria, contact and other relevant information for the research staff.

[name] [name] will conduct the screening, consent, enrollment procedures and all study assessments. She will be trained on the proper conduct of each piece and will be required to practice explaining the consent and administering the study assessments with the co-investigators several times before going into the field. [name] will be responsible for training [name] [name] in proper blood pressure measurement techniques. [name], a bilingual RA will obtain consent. He has previous experience working on

practice-based intervention trials and as part of this work has obtained informed consent from demographically diverse participants.

## **19) Prior Approvals**

N/A

## **20) Recruitment Methods**

Potentially eligible subjects will be recruited in three ways:

1. Providers at the participating site will be asked to identify hypertensive patients in their practices through the use of ICD-9 billing codes. Once a patient is identified who fulfills the inclusion criteria, a letter, signed by the referring provider, will be sent to the patient, explaining the study and providing a telephone number, for him/her to call if s/he is interested in participating. If the patient gets in contact with study staff, the study staff will provide more information about the study (via telephone or in a dedicated space in the clinic). If the patient is interested in participating the study staff will make an appointment with the patient to seek informed consent.
2. Healthcare providers will continue to refer patients during the trial. Healthcare providers as well as nurses, and patient care assistants (PCAs) will be given a card which gives the inclusion criteria; the provider/nurse/PCA will explain to potential participants that there is a study in which s/he might be interested in participating. If the patient expresses interest, the healthcare providers, nurse or PCA will give the patient a card with the study staffs' telephone number. The same follow-up procedures will be used as noted in method 1.
3. Third, to maximize our reach, a random sample of patients who participated in [name] IRB approved project #11-0053 and indicated on the main project consent form that they are willing to be re-contacted in the future will be contacted by [name]. In order to contact these patients, the following information will be obtained from [name] trial: Name, mailing address, and phone number. This information will be used to contact the patients via a postal letter and then by a phone call. The letter will include a brief description of the project and the reason why they are being contacted to participate. It will also provide information about how to get in touch with [name] to schedule an in person visit and it will inform participants that [name] will be contacting them soon via a phone call. During the call the [name] will explain that the purpose of the project and the patient's responsibilities. If the patient expresses interest in completing the survey and agrees to participate at this point, s/he will be scheduled for the consent visit.

In order to randomly select patients to receive an interest letter, each and patient that completed project #11-0053 will be assigned a number. Using a random number table, three patients will be chosen to receive a letter. We will then use the following procedures for each patient: If the first patient chosen

## PROTOCOL TITLE: Tailored Approaches to Improve Medication Adherence

refuses to participate when called, research personnel will approach the second person chosen, and so on until a participant agrees to the project or the list is exhausted. This process will continue until all potential patients are contacted and invited to participate in the study.

### **21) Local Number of Subjects**

Characteristics of the study population:

Forty patients with hypertension will be recruited to participate in this study. Patients will be ages 18 and over and include both males and females. Patients must self-identify as English or Spanish-speaking Latino(a)s or African/American Black (see inclusion criteria in section 4).

### **22) Confidentiality**

To ensure confidentiality, data will be associated with an individual patient only by an assigned identification number, the code for which will be kept in a locked drawer accessible only by the study team. Prior to inclusion in any data set (internal and external), data will be stripped of all identifying information.

### **23) Provisions to Protect the Privacy Interests of Subjects**

During the recruitment, the RA will meet with the potential participants, individually in a private space to give a fuller description of the study in clear, easy to-understand language, including the following: patients will provide informed consent to be enrolled in the study; they have a 50-50 chance of being in either study group; they will be asked permission to have their charts reviewed; and not every patient is accepted into the study (this will be decided during the screening). Permission will also be asked to audiotape the patient education or counseling sessions. Patients giving permission to have the interviews audiotaped will be provided with a separate consent form that will be explained in easy to- understand language and follow the procedures outlined above. Refusal to participate in an audiotaped interview will not limit patients' ability to participate in the study. The protocol and consent form will be approved by the Institutional Review Boards at New York University School of Medicine. During the consent procedures the RA will provide a copy of the consent form for him/her to read; if the participant asks for help, or evidences a problem in reading the consent, the RA will read and explain the consent him/her. If the participant desires to participate, s/he will sign, and the RA will co-sign. If the patient desires to participate in the study at this point, they will be asked to provide written consent. During the consent procedures, the RA will use the following general principles to ensure patient privacy is maintained:

- Use non-medical terminology and simple explanations whenever possible
- Identify the patients' role in the study for which they are being recruited
- Make certain that patients understand that the information they give on a questionnaire or in an interview is confidential.
  - Explain that the patients name will not be on any of the study materials, but rather, a study number and initials identify patients. The patient's

## PROTOCOL TITLE: Tailored Approaches to Improve Medication Adherence

- name will not be attached to the information in any way, even if information is written up about the study later.
- Explain who has access to the information. The patient must be told that others will see the information, but they will be people connected with the study.
- Assure patients that they will not experience any pain or discomfort participating in the interview. Many patients are concerned about additional pain or discomfort; assure the patient that this interview is “talking only”.
- Talk honestly about the role the patient plays in research studies. Explain that although the patient may gain nothing from participation, information learned from his/her participation and that of the other patients may lead to improvements in the treatment of hypertensive patients in the future.
- Assure patients that they have the right to withdraw from the study at any time and that the choice to withdraw will not affect the services that they receive from the clinic in any way.

### **24) Payment of Participation**

Patients will \$20 for participating in the main study and an additional \$10 if they agree to complete an exit interview.

### **25) Cost to Subjects**

There will be no cost to the patient for participating in this study.

### **26) Consent Process**

The required information for informed consent will be summarized orally to the patient by the bilingual RA during the initial in-person contact and will be presented again in a comprehensive written consent/authorization form. The consent process will be conducted in a dedicated space at the primary care clinic. The study staff will adhere to the SOP: Informed Consent Process for Research (HRP-090). Specifically, during the consent meeting, the RA will explain the following study procedures: that patients will have a 50-50 chance of being in the tailored adherence intervention (TAI) or single patient education (PE) session; that they will be asked to give permission for their charts to be reviewed; that participation is completely voluntary, and that not every patient is accepted into the study (this will be decided during the screening).

To ensure comprehension, subjects will be asked to repeat back to the RA the salient points of the consent form to make sure that they understand the study they are agreeing to participate in. If a participant asks for help while reading the consent, or evidences a problem in reading the consent, the RA will read and explain the consent him/her.

If the participants speak Spanish they will receive a Spanish Consent form. The Spanish consent form will be explained by the bilingual RA. A Spanish version of the consent form will be provided to the IRB once the English version is approved.

Statistical Analytic Plan
Tailored Approaches to Improve Medication Adherence
NCT01643473
05/10/2018

Analysis of the qualitative data: [name] and a trained research assistant conducted the qualitative analysis of the audiotaped interview data. Transcripts of the interviews were uploaded to the Atlas.ti program in order to code the data and facilitate content analysis. The transcripts were individually reviewed and analyzed using the grounded theory constant comparison method. Specifically, transcripts were coded line-by-line using open coding (comparing and categorizing data to generate concepts); axial coding (reorganizing data into categories based on relationships within and between these categories); and selective coding (identifying and describing the central themes to generate a conceptual framework) according to issues related to medication-taking (e.g., side effects, cost, forgetfulness). Once the transcripts were independently coded, the research team met to discuss the coding and resolve any discrepancies.

Analysis of study feasibility: We assessed reach of the intervention by examining the ratio of eligible participants invited to participate vs. those that enroll in the study. We also collected data on patients' age and gender to determine if there are any differences between eligible participants that do not enroll vs. enrollees. Independent t-tests and the chi-square statistic were used to determine if there are any significant differences between the groups. Reasons for not enrolling in the program were also documented. In addition to these outcomes, exit interviews were conducted with a subsample of 12 participants to assess acceptability and satisfaction with the program.

Analysis of exploratory outcomes: To test the exploratory aim, we conducted separate differences in differences estimations for each of the outcome measures (i.e., adherence, BP HbA1c) whereby pre-intervention values are subtracted from post-intervention values, and change amounts by study group are compared using t tests. We also conducted linear regression models to examine whether the average baseline scores were significantly different from the average scores at 3 months, when, controlling for baseline levels of the outcome measure (i.e., adherence, BP HbA1c), age, gender socioeconomic status (SES), insurance status and number of medications

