### **Analysis for the Tertiary Aims:**

**The effect of treatment on adherence status at 3-months.** Adherence will be measured as a continuous variable. A linear regression will be performed using the final assessment of adherence as a response and randomization group as a predictor. Other variables that may potentially have an effect on adherence such as age, gender, level of education and comorbidity will also be included if these variables are not balanced between groups by the randomization or if they are determined by univariate analysis to be significantly predictive of adherence.

**The effect of treatment on BP reduction at 3-months.** BP will be treated as continuous systolic BP (SBP) and diastolic BP (DBP) variables measured at baseline and 3-months. The effect of treatment on these variables over time will be assessed using differences in differences estimation whereby pre-intervention SBP and DBP values are subtracted from post-intervention values, and change amounts by study group are compared using t tests. The significance level will be set at  $\alpha=.05$ . Analysis of covariance will be used in place of a t test, if covariates are needed.

**The effect of treatment on HbA1c reduction at 3-months.** HbA1c will be treated as a continuous variable at baseline and 3 months. The effect of treatment on HbA1c over time will be assessed using differences in differences estimation whereby pre-intervention HbA1c values are subtracted from post-intervention values, and change amounts by study group are compared using t tests. The significance level will be set at  $\alpha=.05$ . Analysis of covariance will be used in place of a t test, if covariates are needed.

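### For each exploratory outcome the SAP reports a change-score t test and also an adjusted regression, names neither as main, and words the regression so that it does not test the group effect

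*SAP*

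**What the plan says.** The SAP, dated 05/10/2018, describes completed work. Its paragraph on exploratory outcomes begins "To test the exploratory aim, we conducted separate differences in differences estimations for each of the outcome measures", with change compared between groups by t test. It continues "We also conducted linear regression models", whose purpose is "to examine whether the average baseline scores were significantly different from the average scores at 3 months", controlling for the baseline level of the outcome and for "age, gender socioeconomic status (SES), insurance status and number of medications". It names no main analysis, significance level or group term in the regression. Its feasibility paragraph gives a realised count: "exit interviews were conducted with a subsample of 12 participants". Protocol Section 9 had planned 10.

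Protocol Section 10 (analysis for the tertiary aims) sets one route per outcome:

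- Adherence: linear regression of the final value on randomised group. Age, gender, education and comorbidity are examples of covariates that enter only if unbalanced or predictive. No significance level is given.
- SBP, DBP and HbA1c: t test on change. "The significance level will be set at" .05, and "Analysis of covariance will be used in place of a t test, if covariates are needed".

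**The concern.** The protocol's replacement rule has become an addition in the SAP. Each outcome now has two p-values, and nothing says which one answers the hypothesis. SES, insurance status and number of medications are not named in the protocol's tertiary analyses. The protocol's conditions for adding covariates do not appear in the SAP.

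If both analyses test the group effect, the more favourable one can be reported and the nominal .05 is exceeded. If the regression is what its wording says, a change over time common to both arms could be read as evidence for the intervention. Either way, a reader of a document titled as an analysis plan may take both analyses as fixed in advance. The protocol means these results to lay the groundwork for a larger trial.

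**Working it through.** **Inputs from the documents.** Level .05 for BP and HbA1c (protocol Section 10). 20 patients per group, 15% attrition, about 15 completers per group (Section 10, sample size). Since 20 × 0.85 = 17, both 15 and 17 are used, with 20 as the no-dropout case. The SAP regression has the baseline value plus five covariates.

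**Assumptions not in the documents.** Normal data; equal variance at baseline and 3 months; baseline-to-3-month correlation r of 0.3, 0.5 or 0.7; five covariates unrelated to outcome; two-sided tests.

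**Step 1: the stated level.** One test per outcome gives 1 − (1 − .05) = .05. In simulation under no effect (40,000 trials per setting), the t test alone rejects in 0.0497 to 0.0520 of trials, and the regression with a group term alone in 0.0488 to 0.0513. The Monte Carlo standard error is √(.05 × .95 / 40,000) = 0.0011, so the stated figure is reproduced.

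**Step 2: reading A, the regression contains a group term and either result may be used.** Model: 3-month value = intercept + group + baseline + five covariates. Proportion of null trials in which the t test or the regression has p < .05:

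| Completers per arm | r = 0.3 | r = 0.5 | r = 0.7 |
|---|---|---|---|
| 15 | 0.0851 | 0.0792 | 0.0759 |
| 17 | 0.0834 | 0.0799 | 0.0749 |
| 20 | 0.0796 | 0.0782 | 0.0764 |

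Repeat simulations at 15 and 17 per arm gave 0.072 to 0.085. The result is therefore about .07 to .085 per outcome. Two independent tests would give 1 − .95² = 0.0975, and the Bonferroni ceiling is 0.10.

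**Step 3: reading B, the regression as worded.** It asks whether the 3-month mean differs from the baseline mean and names no group term, so it says nothing about TAI against PE. It is also hard to specify: the baseline value cannot be both the comparator and an ordinary adjustment covariate. As a stand-in, take a paired test in the pooled arms, with no treatment difference but a common mean change of m standard deviations of change. The rejection probability comes from the noncentral t with noncentrality m√n:

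| Completers in total | m = 0 | m = 0.2 | m = 0.3 | m = 0.5 |
|---|---|---|---|---|
| 30 | 0.050 | 0.185 | 0.355 | 0.754 |
| 34 | 0.050 | 0.205 | 0.397 | 0.808 |

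The shifts are assumed. They show that such a p-value can be small with no group effect at all.

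**Step 4: what a single adjusted comparison offers.** With common variance σ², a change score has variance 2σ²(1 − r). Regression on baseline leaves σ²(1 − r²). The ratio is (1 − r²) / [2(1 − r)] = (1 + r)/2, which is 0.65, 0.75 and 0.85 at r = 0.3, 0.5 and 0.7. The adjusted comparison is more precise over this range, before the small cost of one degree of freedom.

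**The case against.** The strongest defence is that these are tertiary outcomes, called exploratory in the SAP, in a pilot with no power calculation, and that adjusted models were foreseen: a group regression with an open covariate list for adherence, and conditional ANCOVA for BP and HbA1c. The protocol was also never a single rigid test, because its data management paragraph adds imputed against complete-case comparisons and logit-score covariates. This stands. It limits the weight of the point, but it does not say which SAP result answers each hypothesis.

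Four stronger readings are tempting, and the documents do not support them:

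- That the SAP contains two group analyses. Only the t test is clearly one; the inflation in reading A depends on a group term that the SAP does not mention.
- That a stated .05 fails for every outcome and across outcomes. The level is given for BP and HbA1c only. Four independent outcomes at .05 give 1 − .95⁴ = 0.185 even with one test each, and nothing promises control of that. For adherence, a choice among three analyses gives about 10.5 to 11.7%. Most of that comes from the separate move from a final-value regression to a change-score t test (about 9 to 10% for those two alone).
- That the models were chosen after seeing outcome data. The past tense and the count of 12 show when the document was written, not when the models were chosen; no data-access date is given.
- That no adjusted model can be called prespecified. What the protocol lacks is running both analyses and this fixed covariate set. The absence of education and comorbidity bears on adherence only, where they were conditional, and the undefined SES variable might include education.

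**Conclusion.** The point holds in limited form. Two analyses are reported per outcome where the protocol provides one route, and neither is named as main. Read literally, the regression does not test hypotheses a to c. Read as a group comparison from which either result may be taken, it raises the error rate for SBP, DBP and HbA1c from .05 to about .07 to .085 each, under the assumptions listed. Which reading applies cannot be settled from the text. The inflation is modest and confined to exploratory outcomes, and the primary and secondary objectives are untouched. It is still worth correcting, because the protocol states directional hypotheses and a significance level for BP and HbA1c.

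**What to change.** In the SAP, name one main between-group analysis per outcome: the 3-month value regressed on randomised group and the baseline value, with the group coefficient and its confidence interval as the result. Beside it, report the protocol's Section 10 analysis for every outcome. Label the five-covariate regression as supportive and not in the protocol, and write out its model, including whether it has a group term. State when each analysis was added relative to data access, and use the term post hoc only where that date shows it. Rest no efficacy statement on the supportive model's p-value.

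This uses data already collected and changes only the SAP and report text. The price is that a significant supportive model can no longer carry a claim. A main analysis named now must also be disclosed as named after the analyses were run; naming it removes the choice between tests from the report but does not restore a prespecified .05.
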